6. DISCONTINUATION OF TREATMENT AND PATIENT WITHDRAWAL

6.1 Discontinuation of study treatment

Patients may be discontinued from investigational product (IP) in the following situations. Note that discontinuation from study treatment is NOT the same thing as a complete withdrawal from the study

- Patient decision. The patient is at any time free to discontinue treatment, without prejudice to further treatment
- Adverse Event
- Severe non-compliance with the Clinical Study Protocol
- Bone marrow findings consistent with myelodysplastic syndrome (MDS)/acute myeloid leukaemia (AML)

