6.1.1 Procedures for discontinuation of study treatment

The investigator should instruct the patient to contact the site before or at the time if Study treatment is stopped. A patient that decides to discontinue Study treatment will always be asked about the reason(s) and the presence of any AEs. The date of last intake of Study treatment should be documented in the CRF (electronic or paper). All Study treatment should be returned by the patient at their next on-site study visit or unscheduled visit. Patients permanently discontinuing Study treatment should be given locally available standard of care therapy, at the discretion of the Investigator.

Any patient discontinuing investigational product should be seen post discontinuation for the evaluations and sample collections outlined in the study schedule.

After discontinuation of the study medication at any point in the study, all ongoing AEs or SAEs must be followed until resolution unless, in the Investigator's opinion the condition is unlikely to resolve due to the patients underlying disease, or the patient is lost to follow up (see Section 7.2).

Clinical Study Protocol - 6
Olaparib - ESR-18-13807

All new AEs and SAEs occurring during the 30 calendar days after the last dose of study medication must be reported (if SAEs, they must be reported within 24 hours as described in Section 8.4.1) and followed to resolution as above. Patients should be seen at least 30 days after discontinuing study medication to collect and / or complete AE information. For guidance on reporting adverse events after the 30 day follow up period see Section 7.3.2.1.

Discontinuation of Study treatment, for any reason, does not impact on the patient's participation in the study. The patient should continue attending subsequent study visits and data collection should continue according to the study protocol. If the patient does not agree to continue in-person study visits, a modified follow-up must be arranged to ensure the collection of endpoints and safety information. This could be a telephone contact with the patient, a contact with a relative or treating physician, or information from medical records. The approach taken should be recorded in the medical records. A patient that agrees to modified follow-up is not considered to have withdrawn consent or to have withdrawn from the study.

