7. STUDY ASSESSMENTS AND PROCEDURES

7.1 Efficacy assessments

7.1.1 Clinical outcome assessments

Evaluate the percentage of patients who develop drug-induced folate deficiency while on olaparib, defined as serum folate level <7 ng/mL.

Determine the impact of folic acid supplementation on anemia, need for transfusion, and dose modification of olaparib as compared to those who did not receive/require folic acid supplementation.

Tumor assessment will be performed as per treating physician's decision and would include regular clinical exams, tumor marker monitoring, and imaging (body CT scans) at every 3 -6 month interval. Tumor response will be evaluated according to treating physician assessment. Response rate is defined as achievement of complete response (CR) or partial response (PR). Progression free survival, PFS, is defined as time from enrolment until disease progression or death. Patients who withdrew from olaparib before disease progression or death will be censored at the date of their last tumor assessment.

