8. STATISTICAL CONSIDERATIONS

8.1 Statistical hypotheses

- Olaparib-treated patients develop folate deficiency
- Replacing folic acid in these patients can mitigate olaparib-induced adverse events related to its hematologic toxicity (anemia, transfusion needs/number of transfusions, dose reductions and drug discontinuation)
- Folate replacement does not affect an antineoplastic effect of olaparib

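### Section 7.1.1 censors PFS when olaparib stops, discarding events that section 6.1.1 wants collected, and at rates that would differ by arm if folic acid reduces discontinuation

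*Combined protocol and SAP*

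**What the plan says.** All references are to the combined protocol and SAP.

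- **PFS (7.1.1).** PFS "is defined as time from enrolment until disease progression or death". The censoring rule follows: "Patients who withdrew from olaparib before disease progression or death will be censored at the date of their last tumor assessment". The trigger is stopping the drug, and the censoring date is a tumour assessment, not the stop date. The rule does not say whether that is the last assessment before stopping or the last one on record.
- **Stopping treatment (6.1).** The section notes that "discontinuation from study treatment is NOT the same thing as a complete withdrawal from the study". The listed reasons include adverse events and the patient's own choice.
- **Follow-up after stopping (6.1.1).** "Discontinuation of Study treatment, for any reason, does not impact on the patient's participation in the study". It continues: "The patient should continue attending subsequent study visits and data collection should continue according to the study protocol". For patients who decline visits, "a modified follow-up must be arranged to ensure the collection of endpoints and safety information".
- **Discontinuation as an outcome (2 and 8.1).** Section 2 makes olaparib discontinuation part of a secondary objective for folic acid. Section 8.1 hypothesises that folic acid mitigates haematologic toxicity, listed as "anemia, transfusion needs/number of transfusions, dose reductions and drug discontinuation". A separate hypothesis is that folate replacement leaves olaparib's antitumour effect unchanged.
- **Analysis (8.4.1).** PFS is compared among patients randomised 1:1, and Kaplan-Meier is the only method named. No sensitivity analysis is planned for patients who stop olaparib.

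**The concern.** The protocol asks sites to keep collecting endpoints after olaparib stops, and then applies a PFS rule under which those endpoints do not count. Missing data do not force this choice.

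It matters most for the randomised comparison. Whether a patient is censored depends on stopping olaparib, which the plan expects folic acid to change. If the plan is right, controls are censored more often. Kaplan-Meier estimation assumes that censored patients have the same later risk as those still followed. Patients who stop for toxicity or by choice may well differ, although the documents give no data on this.

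There is a second effect. If the censoring date is the last assessment before stopping, event-free time already observed on olaparib is removed, and more of it in the arm with more stopping.

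**Working it through.** **The plan's own figures.** No sample size, event count, margin or power is given for PFS. The only sized quantity is the primary endpoint (8.2): null 50%, alternative 66%, one-sided 0.05. With n = 60 and success at 37 or more, the exact binomial gives alpha 0.046 and power 0.802, and 60/0.80 = 75. Both figures reproduce, and this point does not affect them. They cap the randomised comparison at about 75 × 0.66 ≈ 50 patients.

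**Inputs from the documents.** Study end at 7 months (3.4); imaging every 3-6 months (7.1.1); 6% discontinuation for adverse reactions in an earlier olaparib trial (Background, after 1.4).

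**Assumptions not in the documents.** Exponential PFS with median 9 months, so λ = ln 2/9 = 0.0770 per month. A proportion p stops olaparib unless progression or death comes first, at a time S uniform on 0.5-6 months and unrelated to prognosis. The hazard after stopping is k times λ, with k from 1 to 3. Censoring is at the last assessment before stopping, with assessments 3- or 6-monthly.

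**Per-patient quantities over 7 months** (means are over S):

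- Never stops: events a = 1 − exp(−7λ) = 0.4167; time a/λ = 5.411 months.
- Would stop, up to S: events b = 1 − mean[exp(−λS)] = 0.2156; time b/λ = 2.799 months.
- Time removed by back-dating: L = mean[exp(−λS) × (S − last assessment)] = 1.238 months (3-monthly) or 2.397 months (6-monthly).
- Events after stopping: c = mean[exp(−λS) × (1 − exp(−kλ(7 − S)))] = 0.201, 0.279, 0.344 and 0.447 for k = 1, 1.5, 2 and 3.

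**Event rate in an arm**

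- Current rule: [(1 − p)a + pb] / [(1 − p)5.411 + p(2.799 − L)]
- Full follow-up: [(1 − p)a + p(b + c)] / [(1 − p)5.411 + p(2.799 + c/(kλ))]

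The current-rule formula contains neither c nor k, so it cannot respond to anything that happens after stopping.

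Example, 3-monthly assessments:

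- p = 0.30: (0.2917 + 0.0647)/(3.788 + 0.468) = 0.0837
- p = 0.06: (0.3917 + 0.0129)/(5.086 + 0.094) = 0.0781
- Ratio: 0.0781/0.0837 = 0.93

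**Rate ratios, folic acid over control**

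| Stopping, control v folic acid | Full follow-up, k = 1 / 1.5 / 2 / 3 | Current rule, 3-monthly | Current rule, 6-monthly |
|---|---|---|---|
| 20% v 6% | 1.00 / 0.97 / 0.95 / 0.91 | 0.96 | 0.93 |
| 30% v 6% | 1.00 / 0.95 / 0.91 / 0.85 | 0.93 | 0.87 |
| 6% v 3% | 1.00 / 0.99 / 0.99 / 0.98 | 0.99 | 0.99 |

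Simulation of the first two rows under the current rule gave about 0.86-0.97, in agreement. With k = 1 there is no true effect, yet the rule shows an apparent folic acid benefit. With k = 3 and 30% stopping it hides part of a real difference.

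**Events discarded**, pc / [(1 − p)a + p(b + c)]:

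- Control, from p = 0.20, k = 1: 0.0402/0.4167 = 10%, to p = 0.30, k = 3: 0.1342/0.4906 = 27%.
- Folic acid, p = 0.06: 3% (k = 1) to 6% (k = 3).

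**If stopping is related to prognosis.** Separate simulations with a true hazard ratio of 1, median PFS 7 or 12 months, 3-monthly assessments and stopping of 6% v 3%, 20% v 6% or 30% v 10% moved the ratio by a factor of about 0.95 to 1.05. It fell when stopping was independent of prognosis and rose when the two shared strong frailty.

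**Sampling error.** With d events in 1:1 arms, the standard error of the log hazard ratio is about 2/√d. For d = 20 it is 0.447 and the 95% limits are a factor of exp(1.96 × 0.447) = 2.4 either side; for d = 30 the factor is 2.0. Fifty patients at 0.417 events each would give about 21 events.

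**The case against.** **An on-olaparib analysis is defensible.** The plan's only antitumour hypothesis is that folate replacement does no harm, and restricting PFS to time on olaparib is one reasonable way to address it. This stands as a reason to keep that analysis. It does not justify making it the only one, and the back-dated version is not a clean on-olaparib estimate, as the k = 1 column shows.

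**The rule erases a PFS benefit of folic acid.** A reader might infer this, and the documents do not support it. They predict no PFS gain from staying on olaparib. The ratio of exactly 1.00 appears only if patients are censored at the stop date and stopping is unrelated to prognosis; section 7.1.1 uses an assessment date.

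**Censoring is informative.** A reader might state this as fact. It is an inference: reasons for stopping such as toxicity make it plausible, but no data are given.

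**Patients who stop before their first scan get almost no credited time.** This also goes too far. Section 7.1.1 counts clinical examinations and tumour markers as tumour assessment, and section 7.2.2 has monthly examinations. The 6-monthly column is therefore an extreme.

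**The 20-30% stopping rates are high.** The only documented figure is 6%. Section 3.1 gives folic acid to randomised patients who become folate-deficient with haemoglobin below 10 g/dl, whatever their allocation, which narrows any difference between arms. This stands, and is why the 6% v 3% row is shown.

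**The rule may have been meant for withdrawal from the study.** Possibly, but as written it refers to the drug, so the sentence needs correcting on either reading.

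**Conclusion.** The point holds as an inconsistency in the text with a conditional statistical consequence. Sections 6.1 and 6.1.1 require follow-up that section 7.1.1 then leaves out of PFS. If hypothesis 2 in section 8.1 is true, the omission will be unequal between the randomised arms.

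How much this distorts the comparison depends on stopping rates, assessment spacing and post-stop risk, none of which the documents supply. It ranges from negligible at 6% v 3% to the loss of up to about a quarter of control-arm events at 30% v 6%. The direction is not fixed: back-dating favours folic acid, while shared prognosis can push the other way. Even the larger shifts are well inside a confidence interval spanning a factor of 2.0-2.4 either side.

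This should be corrected because it is avoidable and discards scarce events. It does not threaten the primary endpoint or the sample size.

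**What to change.** In section 7.1.1:

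1. Count progression or death as a PFS event whether or not olaparib was stopped.
2. Censor at the last tumour assessment only for loss to follow-up, withdrawal of consent or study cut-off.
3. Keep censoring at olaparib stop as a sensitivity analysis, and state which assessment date it uses.
4. Report the number censored for stopping olaparib by randomised arm in that sensitivity analysis.

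**Cost.** A short edit to one paragraph. Section 6.1.1 already requires the follow-up, and no sample size or treatment rule changes. There are two drawbacks. Later anticancer therapy can influence events after stopping. Tumour assessments are at the treating physician's discretion, and neither table in section 1.1.1 has a row for them, so ascertainment after stopping may be incomplete. Reporting both analyses shows how far the result depends on the choice.

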7.2 Safety assessments

Planned time points for all safety assessments are provided in the SoA.

7.2.1 Clinical safety laboratory assessments

Clinical Study Protocol - 6
Olaparib - ESR-18-13807

Table 7 Laboratory safety variables

Haematology/Haemostasis (whole blood)	Clinical Chemistry (serum or plasma)
B-Haemoglobin (Hgb)	S/P-Creatinine
B-Leukocyte count	S/P-Bilirubin, total
B-Absolute neutrophil count	S/P-Alkaline phosphatase (ALP)
B-Absolute lymphocyte count	S/P-Aspartate transaminase (AST)
B-Platelet count	S/P-Alanine transaminase (ALT)
B-Mean cell volume (MCV)	S/P-Albumin
	S/P-Potassium
	S/P-Calcium, total
	S/P-Sodium
Urinalysis (dipstick, if clinically indicated for)	S/P-Urea or Blood Urea Nitrogen (BUN)
U-Hgb/Erythrocytes/Blood	S/P-Total Protein
U-Protein/Albumin	
U-Glucose	

NB. In case a patient shows an AST **or** ALT $\geq 3 \times \text{ULN}$ together with total bilirubin $\geq 2 \times \text{ULN}$ please refer to Appendix A ‘Actions required in cases of increases in liver biochemistry and evaluation of Hy’s Law’, for further instructions.

7.2.1.1 Coagulation (if clinically indicated)

- activated partial thromboplastin time {APTT} will be performed if clinically indicated
- international normalised ratio {INR} will be performed if clinically indicated. Patients taking warfarin may participate in this study; however, it is recommended that INR be monitored carefully at least once per week for the first month, then monthly if the INR is stable.

Each coagulation test result will be recorded in CRF.

7.2.1.2 Bone marrow or blood cytogenetic samples

Bone marrow or blood cytogenetic samples may be collected for patients with prolonged haematological toxicities as defined in Section 8.4.4.1.3.

Bone marrow analysis should include an aspirate for cellular morphology, cytogenetic analysis and flow cytometry, and a core biopsy for bone marrow cellularity. If it is not possible to conduct cytogenetic analysis or flow cytometry on the bone marrow aspirate, then attempts should be made to carry out the tests on a blood sample. Full reports must be provided by the investigator for documentation on the Patient Safety database. These data are not required to be entered into CRF.

Clinical Study Protocol - 6
Olaparib - ESR-18-13807

7.2.2 Physical examinations

Physical exam will be performed and documented at each monthly visit.

7.2.3 Vital signs

Vital signs will be performed and documented at each monthly visit.

7.2.4 Other safety assessments

7.2.4.1 Serum or urine pregnancy test

Pregnancy tests on blood or urine samples will be performed for women of childbearing potential within 28 days prior to the start of study treatment and on Day 1 of each monthly visit while on the study. Tests will be performed by the hospital's local laboratory. If results are positive the patient is ineligible/must be discontinued from study treatment immediately. Details of the pregnancy tests must be recorded in the patient's medical records.

7.3 Collection of adverse events

The Principal Investigator is responsible for ensuring that all staff involved in the study are familiar with the content of this section.

AE will be reported by the patient (or, when appropriate, by a caregiver, surrogate, or the patient's legally authorized representative).

The investigator and any designees are responsible for detecting, documenting, and recording events that meet the definition of an AE or SAE. For information on how to follow/up AEs see Section 8.3.3.

7.3.1 Method of detecting AEs and SAEs

Care will be taken not to introduce bias when detecting AEs and/or SAEs. Open-ended and non-leading verbal questioning of the patient is the preferred method to inquire about AE occurrences.

7.3.2 Time period and frequency for collecting AE and SAE information

Adverse Events will be collected from time of enrolment throughout the treatment period and including the follow-up period until the last contact.

All SAEs will be recorded and reported to the sponsor or designee within 24 hours. The investigator will submit any updated SAE data to the sponsor within 24 hours of it being available.

Investigators are not obligated to actively seek AE or SAE in former study patients. However, if the investigator learns of any SAE, including a death, at any time after a patient's last visit and he/she considers the event to be reasonably related to the Study treatment or study participation, the investigator may notify the sponsor.

Clinical Study Protocol - 6
Olaparib - ESR-18-13807

The method of recording, evaluating, and assessing causality of AE and SAE and the procedures for completing and transmitting SAE reports are provided in CRF.

7.3.2.1 Adverse events after the 30 day follow up period

For Pharmacovigilance purposes and characterisation, any SAE of MDS/AML or new primary malignancy occurring after the 30 day follow up period should be reported to AstraZeneca Patient Safety regardless of investigator's assessment of causality or knowledge of the treatment arm. Investigators will be asked during the regular follow up for overall survival if the patient has developed MDS/AML or a new primary malignancy and prompted to report any such cases.

At any time after a patient has completed the study, if an Investigator learns of any SAE including sudden death of unknown cause, and he/she considers there is a reasonable possibility that the event is causally related to the investigational product (folate), the investigator should notify the Principal Investigator.

If patients who are gaining clinical benefit are allowed to continue study treatment post data cut off and/or post study completion then all SAEs must continue to be collected and reported to Patient Safety within the usual timeframe. After study treatment completion (i.e. after any scheduled post treatment follow-up period has ended) there is no obligation to actively report information on new AEs or SAEs occurring in former study patients. This includes new AEs/SAEs in patients still being followed up for survival but who have completed the post treatment follow up period (30 days).

7.3.3 Follow-up of AEs and SAEs

After the initial AE/SAE report, the investigator is required to proactively follow each patient at subsequent visits/contacts. All SAE/non-serious AEs/AEs of special interest, will be followed until resolution, stabilization, the event is otherwise explained, or the patient is lost to follow-up

Any AEs that are unresolved at the patient's last AE assessment or other assessment/visit as appropriate in the study are followed up by the Investigator for as long as medically indicated, but without further recording in the CRF. AstraZeneca retains the right to request additional information for any patient with ongoing AE(s)/SAE(s) at the end of the study, if judged necessary.

Any SAE or non-serious adverse event that is ongoing at the time of the 30-day follow up, must be followed up to resolution unless the event is considered by the investigator to be unlikely to resolve, or the patient is lost to follow up. AstraZeneca retains the right to request additional information for any patient with ongoing AE(s)/SAE(s) at the end of the study, if judged necessary

7.3.4 Adverse event data collection

The following variables will be collect for each AE;

- AE (verbatim)
- The date and time when the AE started and stopped

Clinical Study Protocol - 6
Olaparib - ESR-18-13807

- CTCAE grade and changes in CTCAE grade
- Whether the AE is serious or not
- Investigator causality rating against the Investigational Product(s) (no)
- Action taken with regard to Investigational Product(s)
- AE caused patient's withdrawal from study
- Outcome.

In addition, the following variables will be collected for SAEs:

- Date AE met criteria for serious AE
- Date Investigator became aware of serious AE
- AE is serious due to.
- Date of hospitalisation
- Date of discharge
- Probable cause of death
- Date of death
- Autopsy performed
- Causality assessment in relation to Study procedure(s)
- Causality assessment to other medication'
- Description of AE

7.3.5 Causality collection

The Investigator will assess causal relationship between Investigational Product and each Adverse Event, and answer 'yes' or 'no' to the question 'Do you consider that there is a reasonable possibility that the event may have been caused by the investigational product?'

For SAEs, causal relationship will also be assessed for other medication and study procedures. Note that for SAEs that could be associated with any study procedure the causal relationship is implied as 'yes'.

A guide to the interpretation of the causality question is found in the Clinical Study Protocol.

Clinical Study Protocol - 6
Olaparib - ESR-18-13807

7.3.6 Adverse events based on signs and symptoms

All AEs spontaneously reported by the patient or care provider or reported in response to the open question from the study site staff: 'Have you had any health problems since the previous visit/you were last asked?', or revealed by observation will be collected and recorded in the CRF. When collecting AEs, the recording of diagnoses is preferred (when possible) to recording a list of signs and symptoms. However, if a diagnosis is known and there are other signs or symptoms that are not generally part of the diagnosis, the diagnosis and each sign or symptom will be recorded separately.

7.3.7 Adverse events based on examinations and tests

The results from the Clinical Study Protocol mandated laboratory tests and vital signs will be summarised in the CSR. Deterioration as compared to baseline in protocol-mandated laboratory values, vital signs should therefore only be reported as AEs if they fulfil any of the SAE criteria or are the reason for discontinuation of treatment with the investigational product.

If deterioration in a laboratory value/vital sign is associated with clinical signs and symptoms, the sign or symptom will be reported as an AE and the associated laboratory result/vital sign will be considered as additional information. Wherever possible the reporting Investigator uses the clinical, rather than the laboratory term (e.g., anaemia versus low haemoglobin value). In the absence of clinical signs or symptoms, clinically relevant deteriorations in non-mandated parameters should be reported as AE(s).

Deterioration of a laboratory value, which is unequivocally due to disease progression, should not be reported as an AE/SAE.

Any new or aggravated clinically relevant abnormal medical finding at a physical examination as compared with the baseline assessment will be reported as an AE unless unequivocally related to the disease under study, see Sections 8.3.9 and 8.3.10.

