1.4 Study rationale

See Section 1.2.

We have observed folate deficiency in 66% of patients of patients with advanced ovarian and metastatic breast cancer occurring within weeks of treatment initiation with olaparib^{2, 3}. While folate deficiency is a known cause of macrocytic anemia, it has not been previously reported in association with olaparib therapy. Since macrocytic anemia is a known complication of olaparib treatment regardless of the cancer type treated, folate deficiency can occur in these patients too.

Clinical Study Protocol - 6
Olaparib - ESR-18-13807

This study is conducted to assess the prevalence and timing of folate deficiency in patients with ovarian, breast, pancreatic, prostate, and other cancers that may benefit from olaparib as determined by their treating physicians based on their tumor sequencing or germline results. .

As folic acid supplementation has not been studied prospectively in this patient population, this study will also evaluate, in a randomized fashion, the impact of folic acid supplementation on anemia and need for transfusion as compared to a placebo group (i.e. no folic acid supplementation while on olaparib).

Background

Olaparib is generally well tolerated. For instance, in the clinical trial of maintenance olaparib monotherapy in patients with platinum-sensitive ovarian cancer who had had 2 or more lines of platinum-based chemotherapy (Study 19), adverse reactions led to olaparib dose interruption, reduction and discontinuation in 35 %, 26 %, and 6 % of patients, respectively¹³. Olaparib is known to cause hematologic toxicity. In the pooled analysis of multiple clinical trials, the following hematologic side effects were observed: anemia in 37% of patients, Macrocytosis (elevated mean corpuscular volume) is reported in up to 89% of patients treated with olaparib¹³. The manufacturer recommends monitoring blood counts at baseline and monthly thereafter, interrupting treatment until any hematologic toxicity has resolved to \leq grade 1, with additional evaluation if blood counts do not recover after 4 weeks of treatment interruption, including bone marrow and cytogenetic analyses^{5, 6}. Little is known about the etiology of olaparib-induced hematologic toxicity.

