8.4.2 Safety analyses

Tabulations and descriptive summaries of adverse events (AEs) and serious adverse events (SAEs) will be reported as described in Section 8. Adverse events will be compared among the comparator groups of the study.

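### Section 7.3.7 keeps symptom-free, non-serious falls in Hgb, neutrophils or platelets out of the AE record even when they lead to interruption, dose reduction or transfusion, so the AE comparison in Section 8.4.2 under-records haematological toxicity

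*Combined protocol and SAP*

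**What the plan says.** Section 7.3.7 explains that results of mandated laboratory tests will be summarised in the study report, and that deterioration in them "should therefore only be reported as AEs if they fulfil any of the SAE criteria or are the reason for discontinuation of treatment". The treatment meant there is the investigational product. The next paragraph adds a further route: "If deterioration in a laboratory value/vital sign is associated with clinical signs and symptoms, the sign or symptom will be reported as an AE". It prefers the clinical term to the laboratory term and uses anaemia as its example. Table 7 in Section 7.2.1 lists haemoglobin, absolute neutrophil count and platelet count among the laboratory safety variables.

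The second hypothesis in Section 8.1 is worded in terms of adverse events: "Replacing folic acid in these patients can mitigate olaparib-induced adverse events related to its hematologic toxicity". It then lists anaemia, transfusions, dose reductions and discontinuation. Section 8.4.2 states: "Adverse events will be compared among the comparator groups of the study". Section 7.4.4.3 refers to neutropenia and leukopenia as adverse events without any condition about seriousness or discontinuation.

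**The concern.** Haematological toxicity is the trial's subject, and the protocol expects to manage most of it short of stopping treatment. Tables 8 and 9 act on Hgb levels and CTCAE grades, whether or not the patient feels unwell, through supportive treatment, interruption and dose reduction. None of these actions makes the event reportable under the first paragraph of Section 7.3.7.

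What is at stake is the completeness of the AE tables. A cytopenia that is not an AE carries none of the Section 7.3.4 variables: CTCAE grade and its changes, investigator causality, action taken and outcome. No data monitoring committee is planned (Section 8.5.1), so there is no independent review of the laboratory data to make up for thin AE tables.

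**Working it through.** No calculation in the plan depends on this rule, so the main check sets the sections side by side.

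**Routes into the AE record for a mandated laboratory value (Section 7.3.7)**
1. It meets an SAE criterion.
2. It is the reason for discontinuing the investigational product.
3. It comes with signs or symptoms. The sign or symptom is then the AE and the laboratory result is supporting information.

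**Actions provided for cytopenias (Tables 8 and 9)**
- Continue olaparib with supportive treatment such as transfusion: not a trigger.
- Interrupt for up to 4 weeks: not a trigger.
- Reduce the dose: not a trigger.
- Discontinue when counts do not recover (Section 7.4.4.4): a trigger by route 2.

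**Example.** A patient without symptoms has Hgb 7.5 g/dl, is transfused as an outpatient, interrupted, and restarted at a lower dose under the row of Table 8 for Hgb below 8 g/dl. Routes 2 and 3 do not apply. Unless an SAE criterion is met, no AE is recorded. The available text does not list the SAE criteria, so I assume that an outpatient transfusion alone is not serious.

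**What is recorded elsewhere**
- Dose reductions and interruptions, with reasons, go in the eCRF (Section 7.4.4.8).
- Unplanned therapeutic procedures go in the CRF (Section 5.5.1).
- Mandated laboratory results are summarised in the study report (Section 7.3.7).
- Section 8.4.1 compares anaemia, transfusion, interruption, reduction and discontinuation in randomised patients. It does not name neutropenia or thrombocytopenia in that comparison.

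**Size**
- Planned enrolment (Section 8.2): 60 / (1 − 0.20) = 75, as stated.
- Anaemia rate on olaparib: 37%, from the pooled analysis cited in the Background under Section 1.4.
- Expected patients with anaemia: 0.37 × 75 = 27.75, about 28 (0.37 × 60 = 22.2, about 22, without the attrition allowance).
- Let f be the share of these who are symptom-free, non-serious and not discontinued. Patients with anaemia absent from the AE tables = 27.75 × f. The documents do not give f. At f = 0 the loss is 0, at f = 0.5 it is about 14, and at f = 1 it is about 28.
- The Background gives no rate for neutropenia or thrombocytopenia, so no corresponding figure can be formed.

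**Effect on the comparison.** Suppose the same share s of events is captured in two groups with true rates pA and pB. The observed difference is s(pA − pB), which shrinks. The observed ratio is s·pA / (s·pB) = pA / pB, which does not change.

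**The case against.** The strongest defence is that Section 7.3.7 gives its reason. Mandated values are summarised separately, so entering them again as AEs would record them twice. Non-mandated values have no such summary, which explains why clinically relevant changes in those are reportable. This stands: the contrast between the two is not an anomaly in itself.

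The defence also notes that Section 8.1 lists in parentheses essentially the outcomes that Section 8.4.1 compares directly. A reader might infer that the haematological hypothesis cannot be tested. The documents do not support that, because it is tested through dedicated secondary endpoints.

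A reader might also infer that all anaemia leading to transfusion or a dose change is missing from the AE record. That is wrong too. Symptomatic anaemia is reportable, though it may be coded as fatigue or dyspnoea, for example, rather than as anaemia.

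On the discontinuation trigger, Section 7.3.2.1 glosses the investigational product as folate, and a reader might infer that stopping olaparib for anaemia would not count. Section 5 treats olaparib and folic acid together as study treatment, and Section 6.1 uses the term for treatment discontinuation, including for MDS/AML. The wider reading is the more natural one, so the wording is loose rather than restrictive.

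Finally, interruption, reduction and transfusion are often left to investigator judgement, so AE counts triggered by them would depend partly on discretion. That is fair, and the fix allows for it.

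None of this removes the gap. Section 8.4.2 still compares AEs under a rule that omits a class of treated cytopenias, and Section 7.4.4.3 still calls two of these conditions adverse events.

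**Conclusion.** The concern holds for cytopenias that are symptom-free, non-serious and do not lead to discontinuation. These are not reportable as AEs even when they prompt interruption, dose reduction or transfusion, so the Section 8.4.2 comparison under-records them. Section 7.3.7 also needs reconciling with Sections 8.1 and 7.4.4.3. The secondary endpoints are not affected. The gap matters most for neutropenia and thrombocytopenia, where the AE comparison is the only planned between-group comparison that would cover them directly.

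For anaemia the loss is between 0 and about 28 of 75 patients, assuming that the 37% rate applies here. Numbers within any two comparator groups, such as the randomised arms, would be smaller.

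Two stronger readings should be set aside. The Background reports that "adverse reactions led to olaparib dose interruption, reduction and discontinuation in 35 %, 26 %, and 6 % of patients", and a reader might take 6/35 as the share of dose-changing events that the rule retains. Those figures cover all causes in one maintenance trial, and nothing shows that haematological events follow them or how many were symptom-free. A reader might also infer a pull toward no difference. With equal under-recording, absolute differences and precision shrink but the relative comparison need not be biased. The documents do not show that under-recording would differ between groups.

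**What to change.** **Section 7.3.7.** Add to the first paragraph, for example: *A fall in a protocol-mandated haematology value is also reported as an AE when it leads to interruption or dose reduction of olaparib or folic acid, or to a transfusion.* In the existing sentence, replace *the investigational product* with *olaparib or folic acid*. Laboratory changes with no action taken stay excluded.

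**Section 8.4.2.** Add a table by group of the worst CTCAE grade of anaemia, neutropenia and thrombocytopenia, derived from the scheduled CBCs. This does not depend on whether an investigator chose to act. CBC frequency differs by folate and Hgb status (Section 1.1), so show the number of CBCs per patient beside it.

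**Cost.** One sentence, one substitution, AE form guidance and some extra tabulation. There will be more AE entries and a higher reported cytopenia rate. The triggering actions and the CBCs are already collected. The change concerns reporting only and leaves clinical management as it is.
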